Buccal Misoprostol Prior to Myomectomy for Reduction of Intraoperative Blood Loss: A Randomized Placebo-Controlled Trial (NCT02209545)

Principal Investigator:

[name] MD

Department of Obstetrics and Gynecology

Northwestern University Feinberg School of Medicine

[name]

[name]

[contact]

[contact]

Study Drug/Study Device:

Active: Buccal Misoprostol (Cytotec) 400mcg

Placebo: Buccal Pyridoxine (Vitamin B6) 100mg

Funding Source: The Gerbie Professorship

Initial version: 01/14/2019

Amended: 09/09/2020

TABLE OF CONTENTS

1.1	Disease Background	6
1.2	Study Agent(s)/Devices Background and Associated Known Toxicities	6
1.3	Other Agents/Devices	7
1.5	Correlative Studies n/a	7
2.0	STUDY OBJECTIVES.....	7
2.2	Secondary Objectives	7
2.3	Exploratory Objectives n/a	7
2.4	Endpoints.....	7
3.0	PATIENT ELIGIBILITY	7
3.1	Inclusion Criteria.....	8
3.2	Exclusion Criteria	8
4.1	Treatment Dosage and Administration.....	8
4.2	Toxicities and Dosing Delays/Dose Modifications.....	8
4.4	Other Modalities or Procedures None.....	9
4.5	Duration of Therapy.....	9
4.6	Duration of Follow Up.....	9
4.8	Patient Replacement	9
5.0	STUDY PROCEDURES.....	9
5.1	Screening/Baseline Procedures	9
5.2	Procedures During Treatment.....	10
5.3	Follow-up Procedures	10
7.2	Adverse Event Monitoring	13
7.3	Definitions	13
7.4	Steps to Determine If an Adverse Event Requires Expedited Reporting	14
7.5	Reporting Requirements for Adverse Events.....	14
7.6	Unblinding Procedures	15

8.1	Agent/Device: Misoprostol.....	15
11.0	STUDY MANAGEMENT	19
11.1	Conflict of Interest	19
11.2	Registration Procedures	20
11.3	Data Management and Monitoring/Auditing	20
11.4	Adherence to the Protocol.....	20
11.5	Amendments to the Protocol.....	21
11.6	Record Retention	21
11.7	Obligations of Investigators	21

LIST OF ABBREVIATIONS

EBL- Estimated Blood Loss

Hgb- Hemoglobin

Hct - Hematocrit

STUDY SUMMARY

Title	Buccal misoprostol prior to either an abdominal and laparoscopic myomectomy for reduction of intraoperative blood loss: a randomized placebo-controlled trial
Short Title	Buccal misoprostol prior to either an abdominal and laparoscopic myomectomy
Protocol Number	STU00091259
Phase	IV
Methodology	Randomized double-blinded placebo-controlled parallel group trial
Study Duration	12 months
Study Center(s)	Prentice Women's Hospital, Northwestern Memorial Hospital
Objectives	Examine efficacy of buccal misoprostol at reduction in intraoperative blood loss at time of either an abdominal and laparoscopic myomectomy
Number of Subjects	70
Diagnosis and Main Inclusion Criteria	Symptomatic uterine fibroids, desire to retain uterus
Study Product(s), Dose, Route, Regimen	Misoprostol 400mcg buccally
Duration of administration	1 hour pre-procedure – At least 4 hours post-procedure
Reference therapy	Placebo (100mg Vitamin B6 tablets)
Statistical Methodology	Power calculation indicates 35 patients per arm will detect 1 standard deviation difference with 90% power. Fisher's exact test to be used for categorical variables and T test to be used for continuous variables with $P <.05$.

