Mass of fibroids (post-op)	Continuous	Cumulative mass of intramural and subserosal fibroids based on pathology reports -Will be used to account for variability in final models.
Pre-treatment with Lupron, Depo-provera, OCPs	Dichotomous	Pre-operative treatment with Lupron, Depo-provera or OCP's
Intraoperative treatment with vasopressin or tourniquet	Dichotomous	Use of intraoperative vasopressin or tourniquet during myomectomy.

Other	Type	Definition	Use
Uterus size in weeks gestation	Ordinal	Uterus size in weeks gestation per pre-operative physical exam	Table 1 characteristic
History of Gynecologic Malignancy	Dichotomous	If history of gynecologic cancer (uterine, ovarian or cervical cancer), then yes. If not, then no.	Exclude if yes.
Uterine Anomaly	Dichotomous	If septate, unicornuate or bicornuate uterus, then yes. If abnormality is less severe than arcuate uterus or normal then no.	Exclude if yes.
Prior Cesarean Section Cycle	Dichotomous	If prior Cesarean delivery, then yes. If no prior Cesarean delivery, then no.	Table 1 characteristic, stratum-specific sub-analyses
Gravidity	Count	Number of prior pregnancies	Table 1 population characteristic
Gravid	Dichotomous	If number of pregnancies is 1+, then yes If number of pregnancies is 0, then no	Table 1 characteristic, stratum-specific sub-analyses
Parity	Count	Number of prior pregnancies	Table 1 population characteristic
Living children	Count	Number of living children	Table 1 characteristic
Woman's Age (SART categories)	Categorical	Group by age in years at abdominal myomectomy: <30 30-34 35-37 38-39 40-42 43+	Table 1 population characteristic
Race	Categorical	Group by race: White, Black/Africa-American, Hispanic, Asian/Pacific	Table 1 population characteristic

		Islander, American Indian/Alaskan Native, Middle-Eastern	
--	--	--	--

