10.3 Data Analyses Plans

To determine whether women who take a pre-operative dose of misoprostol experience lower blood loss during abdominal myomectomy compared to matched controls who take placebo, we will perform linear regression. We will use this model to assess for the role of numerous covariates, including gravidity, parity and age. Secondary outcomes of percent hemoglobin drop, duration of procedure and length of inpatient hospitalization will be assessed using the T test and further evaluated with multivariate-adjusted linear regression where appropriate. The need for post-operative blood transfusion between groups will be assessed with the Chi-square (Fischer's exact) test. The role of numerous potential covariates will be assessed with Chi-square (Fischer's exact) test for dichotomous variables and T test for continuous variables with $p < 0.05$.

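### The Study Summary gives blood loss a T test and section 10.3 gives it a linear regression with an open covariate list; neither is named as the primary test

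*Combined protocol and SAP*

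**What the plan says.** **Primary outcome.** Section 10.2 calls intraoperative blood loss the primary outcome, and the variable table in 10.1 lists it as continuous. The statistical methodology line of the Study Summary reads "Fisher's exact test to be used for categorical variables and T test to be used for continuous variables", at P<.05. Section 10.3 says of blood loss that "we will perform linear regression", and continues: "We will use this model to assess for the role of numerous covariates, including gravidity, parity and age". The 10.1 table adds, for the mass of fibroids taken from pathology reports after surgery: "Will be used to account for variability in final models". Section 10.1 also stratifies the randomisation by pre-operative fibroid volume, which is not among the covariates that 10.3 names.

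**Secondary continuous outcomes.** Section 10.3 states: "Secondary outcomes of percent hemoglobin drop, duration of procedure and length of inpatient hospitalization will be assessed using the T test", and that they are to be "further evaluated with multivariate-adjusted linear regression where appropriate".

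**Transfusion.** Section 10.3 states: "The need for post-operative blood transfusion between groups will be assessed with the Chi-square (Fischer's exact) test". The Summary assigns Fisher's exact test to categorical variables.

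**The concern.** The stated 5% error rate belongs to one test chosen in advance. Here the primary outcome has two candidate tests in two parts of the same document, and no sentence ranks them. Within 10.3 it is also not said whether the treatment effect is to be read from a model with or without covariates, or which covariates enter. If the result is borderline, the choice could be made after the data are seen, and it could decide whether the trial is reported as positive. Section 1.1 describes the earlier evidence as conflicting, so a borderline result is plausible.

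**Working it through.** **Inputs.** 35 per arm (Summary: 70 subjects); alpha 0.05 (Summary and 10.3), taken as two-sided because sidedness is not stated; planned effect 1 SD with 90% power (Summary and 10.2); transfusion requirement up to 20% (1.4). The documents do not give the share of variance explained by covariates (R²) or a transfusion rate under misoprostol. Both are assumed and shown as ranges.

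**1. The plan's own figure.** For a two-sided comparison of two means, n per arm = 2(1.960 + 1.282)²/1² = 21.02, so 22. The exact t calculation gives 22.02, so 23. The 25 per arm in 10.2 is consistent with this (power 93.4%). At 35 per arm, power for 1 SD is 98.5%, and 90% power corresponds to 0.79 SD.

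**2. When the two tests are the same.** A linear regression on treatment alone is the equal-variance T test. In a check on one simulated data set of 70, both gave p = 0.0746. The conflict therefore arises only when covariates enter, which 10.3 and the 10.1 table both foresee.

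**3. Size of the conflict for blood loss.** Simulated outcome: y = d·treatment + √(R²/3)·(x1 + x2 + x3) + √(1 − R²)·e. The three covariates and e are independent standard normal, there are 35 per arm, and each setting has 8,000 trials. The chance that at least one test is significant is P(T test) + P(regression only).

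| R² | Null: T test | Null: regression only | Null: either | 0.5 SD: power, T test | 0.5 SD: power, regression | 0.5 SD: disagree | 1 SD: disagree |
|---|---|---|---|---|---|---|---|
| 0 | 5.15% | 0.97% | 6.12% | 54.3% | 52.9% | 6.8% | 0.9% |
| 0.1 | 5.20% | 1.71% | 6.91% | 54.1% | 57.0% | 11.6% | 1.3% |
| 0.3 | 5.20% | 2.32% | 7.52% | 54.1% | 67.9% | 22.0% | 1.4% |
| 0.5 | 4.85% | 3.50% | 8.35% | 53.7% | 80.6% | 31.7% | 1.7% |

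The simulation standard error of the largest null figure is √(0.0835 × 0.9165/8,000) = 0.3 percentage points. Across repeat simulations the null figures were 6.4% to 6.9%, 7.5% to 8.0% and 8.2% to 8.4% for R² of 0.1, 0.3 and 0.5.

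**4. Transfusion.** Over all 2×2 tables at 35 per arm, 62 are significant by uncorrected chi-square and not by Fisher, and none the other way. Example: 7/35 against 1/35. Chi-square = 70 × (7 × 34 − 1 × 28)²/(35 × 35 × 8 × 62) = 5.08, p = 0.024; Fisher p = 0.055; Yates-corrected chi-square p = 0.060. The Yates version agrees with Fisher on significance in every table at this size. Exact binomial rejection rates:

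| True rates | Fisher | Uncorrected chi-square |
|---|---|---|
| 20% v 20% | 2.5% | 4.9% |
| 20% v 10% | 12.9% | 21.9% |
| 20% v 5% | 32.8% | 51.7% |

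**The case against.** Section 10.3 is the dedicated analysis section. It gives one method for blood loss and keeps the T test for secondary outcomes, while the Summary is a one-line synopsis by type of variable. The explicit term for adjustment appears in 10.3 only for secondary outcomes, so reading the primary regression as adjusted is an inference. At the planned 1 SD effect the choice hardly matters. All of this stands as a limit on the point. It does not remove it: the document does not say that 10.3 prevails, and the covariate sentence that follows directly makes an adjusted model the natural reading. The inflation also concerns null or smaller effects, not the planned one.

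Three stronger readings are tempting and not supported.

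- *The Summary and 10.3 conflict on transfusion.* A reader might infer this, but 10.3 also names Fisher's exact test. The fault is loose wording inside 10.3, which writes two different tests as one.
- *The freedom to choose also inflates the error rate for transfusion.* Uncorrected chi-square contains every Fisher rejection, so taking the smaller p-value is simply the chi-square test. Its null size is 4.9% at a 20% transfusion rate and 3.6% to 5.7% over rates of 5% to 30%.
- *The secondary continuous outcomes have no ranked analysis.* Section 10.3 puts the T test first and regression after it, and the Summary agrees. The open condition on the regression is imprecise, but making the adjusted model the main analysis there would be a preference, not a correction.

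**Conclusion.** The point holds for the primary outcome. The two parts of the document give different tests for blood loss, and the covariate set in 10.3 is open. The cost is moderate: about 6% to 8% false positives instead of 5% if whichever test is significant is reported, and disagreement in about 12% to 32% of trials at a 0.5 SD effect, against 1% to 2% at 1 SD. These figures assume three independent, normally distributed covariates with R² of 0.1 to 0.5, 35 evaluable patients per arm and two-sided testing. They count only two candidate tests; an open covariate list allows more. Adopting the 10.3 regression unchanged would therefore not settle the matter. For transfusion only a clarification inside 10.3 is needed, and for secondary continuous outcomes the existing order can stay.

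**What to change.** **Blood loss.** State in both the Summary and 10.3: *The single primary analysis of blood loss is a linear regression on randomised treatment, two-sided 5%, adjusted for pre-operative fibroid volume, age, gravidity and parity. The unadjusted T test is a sensitivity analysis.* Fibroid volume is there because it is the stratification factor; the other three are already named in 10.3. Keep post-operative fibroid mass out of this model, because it is measured after randomisation. Two details need settling first. The 10.1 table defines parity and gravidity identically, as a count of pregnancies, so as written they cannot both be estimated: correct the parity definition or use only one. Section 10.1 also mentions fibroid location as a basis for randomisation; if it is a stratification factor, add it.

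**Secondary continuous outcomes.** Keep the T test as the main analysis and label adjusted regression as supportive.

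**Transfusion.** Name one test in 10.3. Fisher's exact test matches the Summary, but the loss of power should be disclosed: 33% against 52% for uncorrected chi-square at 20% v 5%, which is more than slight conservatism.

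**Cost.** For the primary outcome, wording only, plus a few degrees of freedom: four single-term covariates leave 70 − 2 − 4 = 64 instead of 68. If the covariates explained nothing, three of them would cost about 54.3% − 52.9% = 1.4 points of power at 0.5 SD.

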1.4 Rationale

Abdominal myomectomy is a common procedure that comes with risks of significant morbidity, including intraoperative blood loss at time of abdominal myomectomy as well as numerous postoperative complications including an up to 20% requirement for transfusion and 2% reported conversion to hysterectomy. The significant morbidity associated with this procedure has led to studies evaluating multiple interventions to reducing bleeding during myomectomy. A systematic review of the interventions to reduce blood loss at time of myomectomy found significant reductions in blood loss with use of vaginal misoprostol however included only one randomized controlled trial (2). Since this time, other studies have been done that reproduce these findings (6, 7), though sample size in these trials is small and results are inconsistent (8). This study would augment existing data by employing a larger sample size and double-blinded design in a U.S. population. This study would also assess the impact of a route of misoprostol administration that is less invasive for patients (buccal instead of vaginal or rectal) but offers a similar pharmacokinetic profile. Outcomes assessed include estimated blood loss, need for transfusion, prolonged hospitalization, change in postoperative hemoglobin level from preoperative baseline.

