2.2 Secondary Objectives

2.2.1 To determine the effect of 400mcg buccal misoprostol at least one hour pre-procedure on the need for blood transfusion during or in post-operative course for either an abdominal or laparoscopic myomectomy

2.2.2 To determine the effect of 400mcg buccal misoprostol at least one hour pre-procedure on post-operative fever after either an abdominal or laparoscopic myomectomy.

2.2.3 To determine the incidence of adverse effects, if any, of 400mcg buccal misoprostol at least one hour prior to either an abdominal or laparoscopic myomectomy.

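### Fisher's exact test is valid but conservative with about 35 women per arm; an unconditional exact test fixed before unblinding would give the transfusion comparison somewhat more power at the same 5% level (an optional improvement, not an error)

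*Combined protocol and SAP*

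**What the plan says.** The Statistical Methodology row of the Study Summary sets Fisher's "exact test to be used for categorical variables", and the t test for continuous ones, at P<.05. It does not say whether tests are one- or two-sided. Read as written, this covers transfusion and the two dichotomous outcomes in the section 10.1 table, post-operative fever and adverse reaction.

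Section 10.3 assigns a test to one of these only: "The need for post-operative blood transfusion between groups will be assessed with the Chi-square (Fischer's exact) test". That wording treats two tests as one. No mid-p or unconditional exact test appears anywhere.

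Transfusion is the first secondary objective (2.2.1), worded as "the need for blood transfusion during or in post-operative course". The only event rate in the documents is in section 1.4, which speaks of "numerous postoperative complications including an up to 20% requirement for transfusion" after abdominal myomectomy. No target effect or power is stated for transfusion. The power statements in the Summary and section 10.2 concern a standardised difference and haemoglobin.

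**The concern.** Fisher's test conditions on the total number of events. With few events the p-value moves in large steps, so the true error rate falls well below the nominal 5%. At the 20% rate, 35 placebo patients would give about 0.20 × 35 = 7 transfusions, and fewer are expected on misoprostol if it works. This is the range where the steps cost most.

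What is at stake is efficiency on a secondary outcome of direct clinical interest. A result such as 7/35 v 1/35 falls just short of significance with Fisher's test (p=0.055), although another exact test that also holds 5% would call it significant (p=0.038).

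**Working it through.** **Inputs.** 35 per arm and P<.05 (Study Summary); control rate up to 20% (section 1.4). Assumptions: two-sided testing, and misoprostol rates of 10%, 5%, 3%, 2% and 1% as a range, since the documents give none.

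**The plan's own figure.** The only power statement at this size is "35 patients per arm will detect 1 standard deviation difference with 90% power". For a 1 SD difference, n = 2 × (1.960 + 1.282)² = 21.0, so 22 per arm (23 with the t distribution). At 35 per arm, power is Φ(√(35/2) − 1.960) = Φ(2.22) = 98.7%. The stated 90% does not reproduce at 35, but it concerns a continuous outcome and does not affect this point. There is no plan figure for a categorical outcome to reproduce.

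**One table by hand.** For 7/35 v 1/35, with 8 events among 70:
- P(7,1) = C(35,7) × 35 / C(70,8) = 235,358,200 / 9,440,350,920 = 0.02493
- P(8,0) = C(35,8) / C(70,8) = 23,535,820 / 9,440,350,920 = 0.00249
- two-sided Fisher p = 2 × (0.02493 + 0.00249) = 0.055
- uncorrected chi-square = 70 × (7×34 − 1×28)² / (35 × 35 × 8 × 62) = 5.08, p = 0.024

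**True size.** For common event rate π, size(π) = Σ b(x; 35, π) b(y; 35, π) over all tables (x, y) that the test rejects, where b is the binomial probability. All 36 × 36 tables were enumerated. Boschloo's p-value is the maximum over π of the probability that the two-sided Fisher p is no larger than the one observed. At 35 v 35 this amounts to rejecting when the Fisher p is at most 0.0784.

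| Common event rate | Fisher | Boschloo |
|---|---|---|
| 5% | 0.26% | 1.06% |
| 10% | 1.30% | 2.75% |
| 15% | 2.16% | 3.53% |
| 20% | 2.52% | 4.30% |
| Maximum over all rates | 2.94% | 4.80% |

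Uncorrected chi-square reaches 5.74%, so it does not guarantee the level.

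**Why Boschloo in this form never does worse.** Both tests reject when the two-sided Fisher p is small enough. Fisher's own cutoff already keeps size at or below 5%, so the recalibrated cutoff can only be the same or larger. At 35 v 35 it adds 46 rejected tables and removes none. For 7/35 v 1/35 it gives p=0.038.

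**Power at 35 v 35.**

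| Placebo v misoprostol | Fisher | Boschloo |
|---|---|---|
| 20% v 10% | 12.9% | 17.4% |
| 20% v 5% | 32.8% | 41.4% |
| 20% v 3% | 45.6% | 56.7% |
| 20% v 2% | 53.3% | 65.8% |
| 20% v 1% | 62.3% | 75.5% |
| 15% v 2% | 27.2% | 40.8% |
| 10% v 1% | 9.8% | 20.3% |

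At 20% v 5%, Fisher's test needs about 40 to 41 per arm to match Boschloo's test at 35.

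**Sensitivity to the split (placebo/misoprostol).** If the 9 unusable participants in section 10.2 are among the 70, 70 − 9 = 61 remain, about 30/31.

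| Split | Fisher maximum size | Power, 20% v 5%: Fisher | Boschloo |
|---|---|---|---|
| 35/35 | 2.9% | 32.8% | 41.4% |
| 34/36 | 3.8% | 41.8% | 50.0% |
| 33/37 | 3.9% | 44.9% | 46.5% |
| 30/31 | 4.0% | 35.5% | 45.1% |
| 30/30 | 2.7% | 24.1% | 33.5% |

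**The version matters.** The two-sided boschloo_exact in scipy doubles a one-sided version. It agrees with the form above for 7/35 v 1/35, but not in unequal arms. For 4/33 v 0/37 it gives p=0.0546 against Fisher's 0.0446. At 33/37 and 20% v 3% its power is 60.0% against Fisher's 62.5%.

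**The case against.** Fisher's test is valid and standard, and the plan promises no power for transfusion, so nothing the plan states is broken. The choice between conditional and unconditional exact tests is a long-standing matter of preference. All of that stands, and it is why this is an improvement rather than a correction.

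Three stronger readings are tempting, and the documents do not support them.

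- A reader might infer that Fisher's test will always run below 3%. That needs exactly equal arms, which the plan does not secure: randomisation is stratified (10.1), converted cases are dropped from analysis (3.2.7), removed patients may be replaced (4.8), and section 10.2 reports 9 unusable participants. At 34/36 the maximum is already 3.8%, and 7/34 v 1/36 is significant with Fisher's test (p=0.026).
- A reader might infer that a seven-to-one result is bound to be reported as non-significant. That holds at 35/35 only if Fisher's test is the one run. Section 10.3 could also be read as chi-square, which gives p=0.024. That reading does not settle the matter, since uncorrected chi-square can exceed 5%.
- A reader might infer that any Boschloo routine recovers power at no cost. The guarantee belongs only to the version built on the two-sided Fisher p-value.

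It is also fair to say that 20% is an upper figure for abdominal myomectomy while the trial admits laparoscopic cases, so the real rate may be lower and power poor with either test.

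**Conclusion.** The point holds as a low-priority improvement. With two-sided testing and exactly 35 per arm, Fisher's test uses at most 2.9% of the 5% allowed; at 34/36, 33/37 or 30/31 it uses up to about 3.8% to 4.0%. Boschloo's test on the two-sided Fisher p-value keeps the level. At 35 v 35 it adds about 9 points of power for 20% v 5% and between 4 and 5 points for 20% v 10%. At 33/37 the first of these gains shrinks to 1.6 points.

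The change does not rescue the transfusion objective. A halving from 20% to 10% would need about 199 per arm for 80% power (pooled normal formula), and power is 13% or 17% at the planned size. The power figures rest on the 20% control rate and on misoprostol rates that are assumed, not stated.

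**What to change.** Before unblinding, in both the Study Summary and section 10.3, name one test for the between-arm comparison of transfusion, fever and adverse reaction: Boschloo's unconditional exact test, two-sided 5%, with the two-sided Fisher p-value as the test statistic. State that a doubled one-sided version, such as scipy's two-sided boschloo_exact, is not to be used, because it can lose to Fisher's test in unequal arms. Report the risk difference with its 95% confidence interval beside each p-value.

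This takes a line or two of text and needs no extra data or patients. The downside is a less familiar test and a short check that the chosen software implements the stated version.
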